2.10 Axitinib

Axitinib is an oral, potent and selective inhibitor of VEGF (vascular endothelial growth factor) receptors 1, 2, and 3. It is being evaluated for use in solid tumors. VEGF receptors are critical components of the processes leading to the branching, extension, and survival of endothelial cells which form new blood vessels during angiogenesis, an absolute necessity for tumor growth beyond microscopic size. In nonclinical tumor mouse models, twice-daily (BID) oral administration of axitinib demonstrated consistent and significant anti-tumor efficacy (marked inhibitory effect on local and distant tumor metastasis and prolonged animal survival). In multiple animal models, combination of axitinib with various standard chemotherapies (eg, docetaxel or carboplatin) and other antiangiogenic agents (eg, bevacizumab) demonstrated improved benefit compared with single-agent chemotherapeutic/antiangiogenic agents.

The nonclinical safety profile of axitinib has been well characterized through the conduct of single-dose and repeat-dose toxicity studies of up to 39 weeks in duration, and safety pharmacology, genetic toxicity, reproductive and developmental toxicity, and phototoxicity studies. The primary target organ toxicities were observed in the gastrointestinal, hematopoietic, musculoskeletal, and reproductive systems. Additionally, hemodynamic effects (elevated blood pressure, reduced heart rate) were identified from repeat-dosing in conscious, telemetered animals. Axitinib was not identified as a mutagen or clastogen, but considered an aneugen at AUC exposure that exceeds that at the recommended human dose (RHD) of 5 mg BID. While axitinib has relevant UV absorbance with the potential to distribute to sun-exposed tissues, no phototoxicity potential was identified from *in vitro* testing in 3T3 fibroblasts. Many of the findings identified from non-clinical safety testing are consistent with the anticipated pharmacological

response to a VEGFR inhibitor, including the blood pressure changes and effects on ovarian follicles and the growth plate of actively growing animals, which are reliant on angiogenesis for development.

Fertility and developmental effects were also observed, consistent with the effects identified from toxicity studies on reproductive organs and role of angiogenesis in the development of a fetus. In mice, rats, dogs, monkeys, and humans, axitinib appeared to undergo some cytochrome P450 (CYP)-mediated metabolism. In vitro studies demonstrated that axitinib was predominantly metabolized by CYP3A4 and to a lesser extent by CYP1A2, CYP2C19, and UGT1A1. CYP inhibition and induction studies suggest the potential for clinical interactions with substrates of CYP2C8 and CYP1A2. Axitinib and its metabolites were widely distributed into tissues in mice, but were not accumulated or retained for long periods in most tissues. The plasma protein binding was 97%, 98%, and 99% in the mouse, dog, and human, respectively.

In humans, the median recovery of [¹⁴C]axitinib radioactivity in feces was 37.0% and in urine was 22.7% (total recovery = 59.7%) of the total orally administered dose (5 mg). In plasma, the glucuronide was the predominant metabolite and accounted for approximately 50% of the circulating radioactivity. The sulfoxide and unchanged parent drug accounted for approximately 20% of the circulating radioactivity. In feces, the parent drug represented the single most predominant radioactive component (12% of the dose). As of 03 June 2009, 35 studies evaluating the safety, efficacy, and PK of axitinib have been completed or are ongoing. These studies include 11 Phase 1 studies in healthy subjects and 24 studies in subjects with cancer including 1 continued access protocol. Data are available for 24 of these studies.

A study in healthy volunteers (Protocol A4061007) indicated that the mean absolute oral bioavailability of the drug was 58%. Interaction studies in healthy volunteers with ketoconazole (CYP3A4 inhibitor) and rifampin (CYP3A inducer) produced a 2-fold increase and 79% reduction in axitinib plasma exposures, respectively (Protocols A4061004 and A4061026). Axitinib has two major (non-pharmacologically active) circulating plasma metabolites, a glucuronide product and a sulfoxide product (Protocol A4061003). In subjects with moderate hepatic impairment (Child Pugh B), there was a ~2-fold increase in axitinib AUC_{0-∞} and a 1.3-fold increase in axitinib C_{max} compared to subjects with normal hepatic function (Protocol A4061036). No difference in axitinib plasma pharmacokinetics was observed between Caucasian and first-generation Japanese volunteers (n=20 each) (Protocol A4061026). Phase 1 studies in combination with chemotherapeutic/anticancer agents in cancer patients have indicated plasma pharmacokinetics of docetaxel, paclitaxel, carboplatin, capecitabine, gemcitabine, cisplatin, pemetrexed, oxaliplatin, 5-FU, bevacizumab and irinotecan (including SN-38) were similar in the absence and presence of axitinib. Likewise, axitinib plasma profiles and pharmacokinetic parameters were similar in the presence and absence of these coadministered chemotherapeutic/anticancer agents (Protocols A4061019 and A4061020). In all ongoing studies, the starting dose is 5 mg BID axitinib and the dose is titrated up to 7 mg BID and then to a maximum of 10 mg BID in patients tolerating axitinib.

Currently, those subjects who could tolerate axitinib with no adverse events related to axitinib above CTCAE Grade 2 for consecutive 2 week periods are permitted to increase their dose step-wise to 7 mg BID and then to 10 mg BID, unless their BP is >150/90 mm Hg or the subject is receiving antihypertensive medication. All ongoing studies allow axitinib dose reductions to as low as 2 mg BID for > Grade 2 treatment-related adverse events.

Overall, the adverse events reported for axitinib in clinical studies are considered manageable, generally reversible and expected for this class of agents (described in detail herein).

3.0 Patient Eligibility

3.1 Inclusion Criteria

3.1.1 Histologically confirmed diagnosis of prostate cancer

- 3.1.2 High-risk prostate cancer as defined by 1 of the 3 following criteria: (1) baseline PSA > 20, (2) clinical stage \geq T3a, and (3) Gleason score 8-9.
- 3.1.3 Subjects must be appropriate candidates for prostatectomy and pelvic lymph node dissection, as deemed by a multidisciplinary team. Subjects must provide informed consent to these procedures prior to initiating study treatment
- 3.1.4 Subjects must provide written informed consent prior to performance of study-specific procedures or assessments, and must be willing to comply with treatment and follow-up. Procedures conducted as part of the subject's routine clinical management (e.g., blood count, imaging study) and obtained prior to signing of informed consent may be utilized for screening or baseline purposes provided these procedures are conducted as specified in the protocol.
- 3.1.5 Adequate organ function as defined by the following criteria:
 - 3.1.5.1 absolute neutrophil count (ANC) \geq 1500 cells/mm³;
 - 3.1.5.2 platelets \geq 100,000 cells/mm³.
 - 3.1.5.3 Hemoglobin \geq 9.0 g/dL.
 - 3.1.5.4 AST and ALT \leq 2.5 x upper limit of normal (ULN);
 - 3.1.5.5 Total bilirubin \leq 1.5 x ULN;
 - 3.1.5.6 Serum creatinine \leq 1.5 x ULN or calculated creatinine clearance \geq 60 mL/min;
 - 3.1.5.7 Urinary protein <2+ by urine analysis (UA). If UA is \geq 2+ for protein then a 24-hour urine collection can be done and the patient may enter only if urinary protein is <2 g per 24 hours.
- 3.1.6 Male patients, age \geq 18 years.
- 3.1.7 ECOG performance status of 0 or 1.
- 3.1.8 Life expectancy of \geq 12 weeks.
- 3.1.9 No prior systemic therapy for prostate cancer
- 3.1.10 No evidence of preexisting uncontrolled hypertension as documented by 2 consecutive blood pressure readings taken within 1 hour. The baseline systolic blood pressure readings must be \leq 140 mm Hg, and the baseline diastolic blood pressure readings must be \leq 90 mm Hg. Patients whose hypertension is controlled by antihypertensive therapies are eligible.
- 3.1.11 Within 2 weeks of consent (and prior to initiating systemic therapy with axitinib if randomized to that arm), patients should visit with a radiation oncologist to discuss the option of radiation therapy (potentially with concomitant androgen deprivation therapy) for high-risk disease. If the patient has met with a radiation oncologist within 3 months of study enrollment to discuss the possibility of radiation therapy for localized prostate cancer, then this will suffice. Patients do have the right to refuse this consultation; if this is the case, it must be documented by the treating physician in the medical record.

Signed and dated informed consent document indicating that the patient (or legally acceptable representative) has been informed of all pertinent aspects of the trial prior to enrollment.

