2.0 Background

2.1 Defining prognosis in prostate cancer.

Prostate cancer represents the most common malignancy in males, with an estimated 192,280 cases diagnosed in 2009.³ The incidence of prostate cancer rose sharply between 1990 and 1995, likely attributable to an increase in widespread adoption of PSA screening. PSA screening has also resulted in a drastic stage migration in prostate cancer, with far fewer patients presenting with *de novo* metastatic disease.⁴ While these data are encouraging, the increasing proportion of patients with localized disease underscores the need to develop accurate predictive tools to determine the risk of metastatic progression. Clinical guidelines, such as those published by the NCCN, employ risk stratification tools combining stage, grade and PSA to determine the risk of biochemical recurrence after definitive local therapy.⁵ These tools have been validated in several series and provide a superior basis for treatment recommendations compared to clinical stage alone.^{6,7} However, no currently available risk stratification schema has perfect accuracy, and furthermore, only a limited number can predict outcomes outside of biochemical recurrence, such as the risk of metastases and cancer-specific death.^{8,9} Appropriate identification of patients at higher likelihood for such outcomes may provide an opportunity for therapeutic interventions to mitigate this risk.

2.2 Personalizing prognostic models in prostate cancer: The pre-metastatic niche.

The „seed-and-soil“ hypothesis was proposed by Paget in 1889, and suggests that the biological characteristics of certain tissues may foster invasion and growth of metastases.¹ Identification of these susceptible areas, termed pre-metastatic niches, has numerous potential clinical applications. For instance, patients with more abundant niches may have increased metastatic potential – niche prevalence

could therefore serve as a personalized supplement to current prognostic models.² Alternatively, the pre-metastatic niche could act as a target of anticancer therapy, preventing metastases from developing. A necessary precursor to clinical use of the pre-metastatic niche is accurate molecular characterization of this entity. The seminal studies defining the composition of the pre-metastatic niche are described herein.

2.3 VEGFR1⁺ Bone Marrow Derived Cells (BMDCs) initiate the pre-metastatic niche.

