To determine the role of the pre-metastatic niche in prostate cancer, we embarked on a separate retrospective study, specifically examining the predictive role of the niche in the benign lymph nodes of men with high risk prostate cancer. In COH IRB 09213, the City of Hope Prostate Cancer Database (COH Database) was used to identify 46 patients with high-risk PCa (baseline PSA > 20, pT3a-4 disease, or biopsy Gleason 8-10) who had undergone radical prostatectomy and pelvic lymph node dissection (PLND). The COH PCR prospectively collects clinical data associated with patients undergoing prostatectomy at the institution, and warehouses available clinical specimens. Benign tissue specimens (paraffin-embedded) derived from PLND were acquired for each patient, and were stained for VEGFR1 expression. VEGFR1+ cell clusters were counted within 8 distinct 40x fields, and the cluster count was averaged. The average cluster count was 3.13 (standard deviation, 1.43), and ranged from 0-6.25 (see Figure 1). VEGFR1+ clustering in PLND specimens was a significant predictor of biochemical recurrence on multivariate Cox proportional hazards analysis, and outperformed other variables including established prognostic factors such as age, extracapsular spread, seminal vesicle invasion, and the aforementioned high-risk features. Patients with increased VEGFR1+ clustering pelvic lymph node tissue had a shorter interval to biochemical recurrence (HR 0.18, P<0.10). These preliminary results indicate that increased VEGFR1+ cell clustering in benign nodal tissue may predict poorer clinical outcome in patients with high-risk PCa. Our dataset is consistent with a recent report from Fujita *et al* (*Cancer Sci* 2009; 100(6):1047-50), which also suggested that VEGFR1 staining in pelvic lymph nodes predicted the risk of biochemical recurrence after radical prostatectomy in a more heterogeneous group. Together with our dataset, there is emerging rationale for examining VEGFR1 as a key component of the pre-metastatic niche.

Figure 1. Distribution of VEGFR1 clustering in the pelvic lymph nodes of 46 patients with lymph node negative prostate cancer who have been treated with definitive surgical intervention. The number of clusters visualized in 8 40x fields was averaged.

2.8 Preliminary Data: VEGF-TKIs have demonstrable efficacy in the setting of prostate cancer, and have been employed in neoadjuvant trials.

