4.1.1.2 Baseline CT or MRI scan of the abdomen and pelvis

4.1.2 Assessments within 2 weeks of the first dose

4.1.2.1 Demography: date of birth, race and gender.

4.1.2.2 Medical history:

4.1.2.2.1 Prostate cancer-specific history including: date of diagnosis, current stage of cancer, prior systemic treatment for prostate cancer (an exclusion criterion); and history of other malignancies

4.1.2.2.2 Prior surgery and/or radiotherapy (date, organ/anatomic region(s) of surgery and/or radiotherapy must be documented), other significant medical and surgical histories within the past 6 months.

4.1.2.3

4.1.2.4

4.1.2.5 Physical examinations: height (only recorded at baseline) and body weight and current medical conditions.

4.1.2.6 Vital signs: body temperature, blood pressure and heart rate. **Note:** If a subject presents with poorly controlled hypertension, defined as SBP ≥ 140 mmHg or DBP ≥ 90 mmHg, antihypertensive medication(s) should be initiated or adjusted with a goal to control the blood pressure to $< 140/90$ mmHg.

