14.0 Statistical Considerations

14.1 Study Design

14.1.1 The study is an open label, randomized phase II assessment of axitinib as pre-surgical therapy in high risk prostate cancer. In particular, a permuted block randomization scheme will be carried out to achieve treatment/control balance. To avoid selection bias, the blocking scheme will be masked to the principal investigator. The number of blocks will be determined by stratifying high risk patients according to PSA levels (≥ 20 or not) and Gleason scores (≥ 8 or not). For each block, we will randomly choose one arrangement from all possible realizations.*Primary Endpoints*: The primary endpoint of this study is pre-metastatic niche density, as defined by the average number of VEGFR1 clusters in 8 distinct 40x microscopic fields. We will use a two sample student's T-test to compare the primary endpoint of pre-metastatic niche density in the regional lymph nodes of patients treated with axitinib, as compared to the pre-metastatic niche density in the lymph nodes of patients enrolled on the control arm. With a sample of 22 patients per group, we will have 80% power to determine significance across groups if the average niche density is 3.13 in patients in the control arm, and at most 2.19 in patients treated with axitinib, with a common standard deviation 1.43 using a one-sided t-test assuming a type I error = 10% (Calculated using nQuery Advisor 6.01) Taking this into consideration, 30 patients per group will be recruited according to an empirical replacement rate of 27%. The intention-to-treat analysis will be the primary analysis conducted to obtain unbiased comparisons between the treatment and control. In addition, some as-treated subgroup analysis would also be investigated if necessary.*Secondary Endpoints*: Toxicity, time to biochemical recurrence, time to metastatic recurrence. With respect to secondary endpoints, Cox regression will be used (with the log-rank test) to compare time to biochemical recurrence (PSA ≥ 0.2), TTP and OS in patients treated with axitinib to patients treated with surgery alone. The Chi-square test will be used to compare the pStat3, LOX expression and MDSC density in patients treated with axitinib to patients treated with surgery alone. Descriptive statistics will be used to compare serum levels of VEGF-A, sVEGFR2, PDGF-AB and pSTAT3 at various timepoints during therapy.

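### The Cox comparison of time to biochemical recurrence names no baseline covariate, so a chance imbalance in clinical stage, which is not a stratification factor, carries into the estimated hazard ratio

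*Combined protocol and SAP*

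**What the plan says.** - **Eligibility (section 3.1.2).** A man enters on any one of three features: "High-risk prostate cancer as defined by 1 of the 3 following criteria: (1) baseline PSA > 20, (2) clinical stage" T3a or higher, and (3) Gleason score 8-9.
- **Data collected (section 4.1.2.2.1).** The screening history includes "date of diagnosis, current stage of cancer, prior systemic treatment for prostate cancer (an exclusion criterion"), so clinical stage is known for every man before treatment.
- **Randomization (section 14.1.1).** "a permuted block randomization scheme will be carried out to achieve treatment/control balance", with blocks set by "stratifying high risk patients according to PSA levels (≥ 20 or not) and Gleason scores (≥ 8 or not"). Stage is not listed.
- **Analysis (section 14.1.1).** "Cox regression will be used (with the log-rank test) to compare time to biochemical recurrence (PSA ≥ 0.2), TTP and OS" between the arms. No covariate or stratum is named, not even the two stratification factors.
- **Prognosis (section 2.1).** Clinical guidelines are said to "employ risk stratification tools combining stage, grade and PSA to determine the risk of biochemical recurrence after definitive local therapy".

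No other section adds stage to the randomization or to the model.

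**The concern.** Secondary objective 1.2.2 asks whether axitinib prolongs time to biochemical recurrence. The documents themselves link stage to the risk of that outcome, and they make stage one of three routes into the trial. Yet stage is controlled neither by the randomization nor by the model. In a trial of about 60 men the arms can differ in the share with T3a or higher disease, and an arm-only Cox model credits that difference to treatment. If this is noticed after the data are in, any adjustment becomes a post hoc choice in an open-label trial.

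**Working it through.** **1. The plan's own figures.** Section 14.1.1 sizes the trial on niche density. The standardized difference is (3.13 - 2.19)/1.43 = 0.94/1.43 = 0.657. With 22 per arm and one-sided 10%, the noncentral t gives power 0.81, against the stated 80%. Allowing for 27% replacement, 22/(1 - 0.27) = 30.1, so about 30 per arm and 60 in total. This reproduces. For biochemical recurrence the documents give no event count, HR or power.

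**2. Assumed inputs.** 60 men; blocks of 4 in the four PSA-by-Gleason strata; 38-55% with T3a or higher; stage HR 1.5-3; PSA and Gleason HR 1.7-1.8 each; about 30-45 events; one-sided 10% testing, as for the primary endpoint.

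**3. Where stage is left to chance.** A man with PSA below 20 and Gleason below 8 can qualify only on stage, so that stratum is all T3a or higher and the blocks balance it. In the other three strata nothing controls stage.

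**4. How often the arms differ.** With no control at all, the SD of the between-arm difference in stage is sqrt[4p(1 - p)/(2n - 1)]. For n = 30 per arm and p = 0.4 this is sqrt(0.96/59) = 0.128. Simulation with the stratified blocks gives 0.11-0.12. A 15-point difference is then 0.15/0.12 = 1.25 to 0.15/0.11 = 1.36 SDs, a two-sided chance of about 21% to 17%. Simulated frequencies were 16-22%, so about 20%.

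**5. How far the HR moves.** With no treatment effect, the arm-only HR early in follow-up is roughly [1 + a(h - 1)]/[1 + b(h - 1)], where h is the stage HR and a and b are the shares with T3a or higher. Take a = 0.475 and b = 0.325 (15 points apart, mean 0.40):

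| Stage HR | Calculation | Factor |
|---|---|---|
| 1.5 | 1.2375/1.1625 | 1.06 |
| 2 | 1.475/1.325 | 1.11 |
| 3 | 1.95/1.65 | 1.18 |

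Over the whole of follow-up, simulation gives about 6-16%. The low end is soft: one run at stage HR 1.5 and 60 men gave a factor of 1.054 for 20 points, which is 1.054^0.75 = 1.04 for 15 points. With stage in the model, even a 20-point imbalance leaves a factor of only about 1.01-1.06.

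**6. Against the noise.** The SE of the log HR is about 2/sqrt(events): 0.365 at 30 events and 0.316 at 40. The shift is ln 1.06 = 0.058 to ln 1.16 = 0.148, that is 0.058/0.365 = 0.16 to 0.148/0.316 = 0.47 of an SE.

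**7. What adjustment does (simulated Wald tests, 60 men).**

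| | Arm only | Plus stage | Plus stage, PSA, Gleason |
|---|---|---|---|
| Type I error, nominal 10% | 9-10% | about 10% | 10-12% |
| Average HR when the truth is 0.50 | 0.51-0.54 | 0.50-0.51 | 0.47-0.48 |
| Power, stage HR 2 | 68% | 69% | 72% |
| Power, stage HR 3 | 71% | 73% | 76% |

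Stage alone removes most of the pull toward 1. The four-term model overshoots slightly, and part of its apparent power gain is its looser type I error.

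**The case against.** The arms are randomized, so the arm-only comparison needs no covariate to be valid. Its mean log HR is about 0 under the null, its type I error is nominal, and chance stage imbalance is already part of its standard error. About 80% of trials would not show a 15-point difference. Leaving a third factor out of the stratification at 60 men is ordinary practice, and the endpoint is secondary and unpowered. All of this stands, and it limits the weight of the point.

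Three stronger readings are tempting, and none is supported:

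- **That the hazard ratio is biased or the test invalid.** It is not. The issue is chance imbalance within the one trial that is run.
- **That section 2.7 shows clinical stage to be prognostic in the sponsor's own cohort.** It speaks of "established prognostic factors such as age, extracapsular spread, seminal vesicle invasion, and the aforementioned high-risk features", but the stage feature there is pT3a-4, which is pathological. Section 2.1 is the proper support.
- **That adjusting for stage would buy useful power.** The gain from stage alone is about 0-5 points, and it does not reduce the standard error.

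What the objection does not answer is that 14.1.1 specifies no covariates at all, although the trial collects a factor that its own background ties to this outcome.

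**Conclusion.** The point holds as a modest gap in prespecification. Clinical stage defines eligibility, is recorded for every man and is linked by section 2.1 to biochemical recurrence. It is left to chance in three of the four strata and is absent from the Cox comparison. The likely cost is an HR displaced by about 6-16% in the roughly one trial in five with a stage difference of 15 points or more, which is under half of a standard error. That size rests on assumed stage prevalence, stage HR, event count and follow-up. With a weak stage effect the shift could be nearer 4%. With 44 men, the synopsis sample size, imbalances would be somewhat more frequent. The primary endpoint is not affected. This is an improvement worth making, not a threat to the trial.

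**What to change.** In section 14.1.1, state that the Cox hazard ratio for time to biochemical recurrence will be adjusted for clinical stage (T3a or higher, yes/no) and for the two stratification factors (PSA 20 or higher, yes/no; Gleason 8 or higher, yes/no). Keep the log-rank test as the significance test: with about 30-40 events the Wald test from the four-term model is slightly liberal, at about 10-12% for a nominal 10%. Use clinical stage, not pathological stage, because the latter is read after axitinib.

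The cost is one sentence, with no new data, visits or patients. The hazard ratio becomes conditional on the covariates, has a slightly larger standard error and tends in small samples to overstate the effect a little (0.47-0.48 when the truth is 0.50). Because the log-rank test stays unadjusted, the p-value and the adjusted hazard ratio could differ slightly in emphasis, and the report should say so.

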5.1 Registration Requirements/Process

To register a patient, the treating physician should contact the protocol nurse or the responsible Clinical Research Associate (CRA) in Clinical Trial Office (CTO) to complete the eligibility/registration form. The protocol nurse or CRA will contact the Data Coordinating Center at the City of Hope [contact], [name] or e-mail [contact]), EMAIL a copy of the completed eligibility checklist, required pre-study tests (per protocol – and may include laboratory, CT and pathology reports), signed Informed Consent, signed Patients' Bill of Rights and HIPAA authorization form to [contact].

Registration Process The patient registration process will be handled by the Department of Clinical Research Information Support (CRIS) Data Coordinating Center (DCC) at City of Hope. The steps below are to be taken when registering a **patient**:

- The research staff must assure they have the most current and updated version of the protocol and informed consent prior to enrolling a patient. If a question arises, please contact the Data Coordinating Center at [contact] [name] or via email at [contact].
- The study staff must assure that all prestudy laboratory tests, scans and x-rays have been completed prior to registration according to the study calendar
- The study staff must assure that the patient has signed an approved informed consent prior to registration/randomization, including the Experimental Subject Bill of Rights and appropriate HIPAA authorization.
- The study staff must confirm that the patient meets all inclusion and exclusion eligibility criteria for the protocol. The eligibility checklist (provided by the COH DCC) must be completed in its entirety.
- Patients must be registered prior to initiation of treatment but no more than 5 working days prior to planned start of treatment. A patient failing to meet all protocol requirements may not be registered.
- Once a patient is eligible, all the pre-study requirements have been fulfilled, and the informed consent obtained, the research nurse or the data manager (study coordinator) will inform the COH Data Coordinating Center at [contact], [name]; email [contact] and FAX ([contact]) a copy of the patient's signed informed consent, completed eligibility checklist and corresponding source documentation confirming eligibility (including pathology reports, lab reports, x-ray reports, etc.).

The City of Hope Data Coordinating Center will:

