6.6.4 Other Treatments Allowed on Study

Surgery (outside of the mandated prostatectomy and pelvic lymph node dissection), androgen deprivation therapy and radiation therapy are not permitted prior to the time of prostatectomy and pelvic lymph node dissection. However, after prostatectomy, these modalities may be used as clinically indicated. Use of these modalities will be recorded in the data capture form.

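### Inclusion criterion 3.1.11 permits the radiation-oncology consultation after the open-label arm is known, with a looser limit for control men, and is not reconciled with section 5.1.

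*Combined protocol and SAP*

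**What the plan says.** **Timing of the consultation.** Section 3.1.11 sits in the inclusion list. It says that "patients should visit with a radiation oncologist to discuss the option of radiation therapy", and gives the time limit as "Within 2 weeks of consent (and prior to initiating systemic therapy with axitinib if randomized to that arm"). Randomisation is not named as a limit.

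**Exceptions in the same criterion.** An earlier visit counts: "If the patient has met with a radiation oncologist within 3 months of study enrollment", no new one is needed. Refusal is also allowed: "Patients do have the right to refuse this consultation", provided that it is documented.

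**Eligibility check.** Section 5.1 says "The study staff must confirm that the patient meets all inclusion and exclusion eligibility criteria for the protocol", and adds "A patient failing to meet all protocol requirements may not be registered". The coordinating centre reviews the source documents, registers and randomises centrally, and reports the arm to study staff within 24 hours of a complete packet. On timing, section 5.1 also says "Patients must be registered prior to initiation of treatment but no more than 5 working days prior to planned start of treatment".

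**What depends on surgery.** The primary endpoint is counted in benign lymph-node tissue (sections 9.1 and 11.1). Under section 6.6.4, "androgen deprivation therapy and radiation therapy are not permitted prior to the time of prostatectomy and pelvic lymph node dissection". Section 14.1.1 describes an open-label trial with an intention-to-treat primary analysis and gives no rule for a randomised man without a specimen.

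**The concern.** The consultation puts the alternative to prostatectomy to the patient. Held before allocation, it can lead a man to choose radiotherapy at no cost to the comparison, because he is never randomised. Held after allocation in an open-label trial, the same choice leaves a randomised man whose primary endpoint can never be measured. The decision could then be influenced by the arm he was given, and the time limit itself differs by arm. An intention-to-treat label does not restore a specimen that was never taken, so loss that differed between arms could distort the comparison of mean niche density.

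**Working it through.** **1. Does the wording allow a visit after allocation?**

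- Section 5.1 has registration and randomisation handled together, and registration must come before treatment starts.
- If the visit always had to precede randomisation, it would automatically precede the first axitinib dose. The clause about the first dose for men in that arm would then add nothing. It has a purpose only if the visit may follow allocation.
- Section 4.1 also foresees a man who is randomised and then found ineligible, so the protocol does not treat eligibility as always final at randomisation.
- Section 5.1 points the other way, since it requires every criterion to be confirmed at registration.

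Section 3.1.11 thus permits an order that section 5.1 excludes, and neither section refers to the other.

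**2. How do the limits compare by arm?**

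| | Axitinib | Control |
|---|---|---|
| Limit in 3.1.11 | 2 weeks from consent and before the first dose | 2 weeks from consent |
| Day 1 (section 4.1.3) | First dose | Date of surgery |

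For an axitinib man, registration is at most 5 working days before planned treatment, so the gap between allocation and the limit is short. Section 3.1.11 gives control men no corresponding second limit.

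**3. The plan's sample size.** Inputs from section 14.1.1: means 3.13 and 2.19, SD 1.43, one-sided alpha 10%, 22 per group, 80% power.

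- Difference = 3.13 − 2.19 = 0.94.
- Noncentrality = 0.94 / (1.43 × √(1/22 + 1/22)) = 2.18, on 42 degrees of freedom; one-sided 10% critical value 1.302.
- Exact power = 81.0% at 22 per group, and 79.6% at 21. The plan's 22 is reproduced.
- Inflation: 22 / (1 − 0.27) = 30.1, against the stated 30 per group (1 − 22/30 = 26.7%).

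**4. Power if men leave.** Each man is 1/30 = 3.3% of an arm. At assumed rates of 5%, 10% and 20%, that is 1.5, 3 or 6 men of 30. The same exact formula gives:

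| Evaluable men (arm 1 / arm 2) | Power |
|---|---|
| 30 / 30 | 89.4% |
| 30 / 26 | 87.6% |
| 30 / 24 | 86.4% |
| 30 / 22 | 85.1% |
| 22 / 22 | 81.0% |
| 22 / 18 | 77.8% |
| 18 / 18 | 74.7% |

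Power falls below 80% only if the allowance of 8 per arm has already been used up by other losses.

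**5. Bias if leaving is selective (illustration only).** Assume that a fraction f of control men leave and that their mean density is k SDs below that of all randomised control men. The observed control mean then rises by f × k × 1.43 / (1 − f).

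- f = 0.10, k = 0.25: 0.10 × 0.25 × 1.43 / 0.90 = 0.04 clusters, or 4% of 0.94. With no true effect, one-sided type I error is about 12% (30 versus 27 men).
- f = 0.20, k = 0.5: 0.20 × 0.5 × 1.43 / 0.80 = 0.18 clusters, or 19% of 0.94. Type I error is about 20% (30 versus 24 men).
- f = 0.27, k = 1.0: 0.27 × 1.0 × 1.43 / 0.73 = 0.53 clusters, or 56% of 0.94. Type I error is about 51% (30 versus 22 men).

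Neither f nor k comes from the documents. If the leavers have higher density, the sign reverses. If leaving is unrelated to density, there is no bias.

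**The case against.** The strongest reply is that section 5.1 already does the work. It bars registration of a man who does not meet every requirement, and the coordinating centre checks the source documents first. A site that holds the visit, relies on one from the prior 3 months, or documents a refusal before registration complies with both sections. That stands. A reader might infer that the two sections cannot both be followed, and the documents do not support this. The defect is that 3.1.11 does not require the order that makes them agree.

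The exposed group is also limited. The criterion is worded as a recommendation, an earlier visit suffices, and refusal is allowed. Men must already be judged candidates for prostatectomy by a multidisciplinary team (3.1.3), alternatives are explained at consent (5.0), and an operative date is verified (4.1.2.9). This stands too: it limits how often the problem can arise but does not remove the route.

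A reader might also take the control arm to have a full 14 days after allocation. The two weeks run from consent, and screening and packet review come in between, so the interval after allocation is shorter by an amount that the documents do not give.

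Lastly, men may withdraw at any time (15.7), so earlier timing cannot prevent every departure after allocation. That is correct. The change removes one foreseeable cause only.

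Omission of the criterion from the synopsis carries little weight, because that list is presented as a summary.

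**Conclusion.** The point holds as one of timing and consistency. Section 3.1.11 permits the consultation after the arm is known and sets a looser limit for control men. Section 5.1 implies that it must come earlier, and the protocol does not reconcile the two. For a man with neither a recent visit nor a refusal, this leaves an avoidable route from allocation to a missing primary endpoint.

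The size is unknown. The documents give no rate of switching to radiotherapy and no evidence that switching depends on the arm or on niche density. A reader might infer that differential loss is to be expected, or that the trial would be underpowered. Neither is shown. Power stays at 85.1% even with 8 men lost from one arm of 30, and the type I error range of about 12% to 51% follows wholly from assumed inputs. The sample size needs no change on this account. The case for acting is that the amendment is cheap and moves a predictable treatment decision ahead of allocation.

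**What to change.** Reword 3.1.11 so that, in both arms, one of three things is recorded on the eligibility checklist before registration/randomisation: the radiation-oncology visit, the qualifying visit within the prior 3 months, or the documented refusal. Delete the clause that applies only to men allocated to axitinib. Section 3.1.11 then agrees with section 5.1.

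**Cost.** One amended sentence and one checklist line. No visit is added, because the consultation is already in the protocol, and the patient's right to refuse is unchanged.

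**Downside.** Men not covered by the 3-month rule or a refusal may wait a few days for randomisation. The window is tight. Section 4.1.2.9 gives a usual wait of 5–6 weeks from biopsy to surgery, which is 35–42 days. Taking off 28 days of drug and 2 days of washout leaves about 5–12 days for consent, screening and registration. Withdrawal after allocation also remains possible for other reasons.
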